1.3 Research Design and Methods

Bright IDEAS-YA will be tested with young adult cancer patients in a two-arm parallel randomized controlled trial (RCT) of the intervention versus enhanced usual psychosocial care.

A. Research Procedures

Research staff will collect participants' contact information for tracking and study management. Following consent, baseline surveys (see section 1.9 Data Collection) will be administered online using DatStat, a HIPAA-compliant electronic data capture system. Research staff will either provide a tablet for patients to complete the online survey (paper copies will be available as back-up in the event of significant internet disruption) or email/text a link for completion. If a participant does not complete the baseline survey during an initial in-person visit, we will email a link for completion. After completion of the baseline survey, participants will be randomly assigned 1:1 to either the intervention or enhanced usual psychosocial care comparison group. The study biostatistician will determine a randomization scheme stratified by site, age group (18-29 vs. 30-39 based on definitions of emerging adults and young adults¹⁸)using an undisclosed block size to balance group assignment within each site and age group. This schema will be uploaded to the DatStat program such that completion of the baseline survey will trigger assignment according to the schema via a message to study staff. Participants will then be notified of assignment via an automatic Welcome email through DatStat. For those assigned to the intervention group, study staff will assign a Bright IDEAS-YA trainer, schedule for the participant and trainer to meet at the patient's next medical visit or schedule a virtual meeting to complete the first Bright IDEAS-YA session, and mail/email Bright IDEAS-YA manual, worksheets and the list of resources from the NCCN adolescent and young adult patient guildeline. 19 For those assigned to the enhanced usual psychosocial care group, study staff will mail/email the list of resources from the NCCN adolescent and young adult patient quidelines. 19 All participants will also be mailed a small gift (e.g., Bright IDEAS stress ball) as a token of appreciation for their time and effort. Trainers will schedule all subsequent sessions directly with participants. All participants will be asked to complete surveys at 3 months (post-intervention), 6 months (3-month follow-up), 12 months (9-month follow-up), and 24 months (21-month followup). DatStat will send survey links and subsequent reminders via email/text according to the survey schedule. Study staff will also call and/or send text message reminders to participants to facilitate completion of online surveys as needed. All participants will continue to receive usual psychosocial care per institutional standards, as well as a standardized list of young adult-specific resources (see Enhanced Usual Psychosocial Care section). Usage of these services will be tracked via patient self-report at each survey. Participants will receive \$25 for each of the first four surveys completed, and a \$50 gift card for completing the final survey (up to \$150 total).

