- o Financial strain, a marker of socioeconomic status particularly relevant for young adults with cancer, will be measured using the Comprehensive Score for Financial Toxicity (COST),³⁴ an 11-item scale of financial toxicity associated with cancer treatment. Respondents rate each item on a 5-point Likert scale from 0 (*not at all*) to 4 (*very much*) in the past 7 days. The measure yields a total summary score, with higher scores indicating greater financial strain. It has demonstrated adequate internal reliability and face validity.³⁴ These items will be administered at baseline, 12 months, and 24 months. Given that young adults may demonstrate different levels of financial independence, those who indicate that they are not primarily responsible for paying for their medical care will respond to only two items regarding financial stress at baseline only. Those who indicate financial responsibility at baseline and everybody at 12 months, and 24 months follow-up, will respond to the full 11-item scale.
- Oncology Screening Tool, which is an adapted version of the NCCN Distress Thermometer and problem checklist to include problems specific to young adults. Participants first rate their distress on a 0-10 scale. Next, they are asked to check off areas of concern from the past week, including practical (e.g., housing arrangements, work, bills, transportation), family (e.g., parents, siblings, partner), emotional (e.g., sadness, isolation, guilt), social (e.g., isolation from friends, missing important events), physical (e.g., body image, sexual concerns, sleeping difficulty), and informational (e.g., understanding information, feeling involved in decision-making) needs. A total score from 0 to 51 is calculated. This checklist is used to prompt selection of problems to be addressed in the intervention for those assigned to receive the intervention.
- Demographic/Medical: Patients will report age, sex, independent living status, race, ethnicity, school/work status, health insurance coverage, marital status, whether he/she is a parent, and income. Potentially time-varying characteristics (i.e., school/work status, insurance status, income) will be repeatedly assessed at all follow-up surveys. Cancer diagnosis, date of diagnosis, and treatment received (e.g., chemotherapy, radiation, hematopoietic stem cell transplant), will be abstracted from the medical record by research staff. This information will be used to describe the sample and used as

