6.0 Data Management Plan

6.1 Data Analysis

Aim 1: Efficacy of the Bright IDEAS-YA intervention vs. enhanced usual psychosocial care will be evaluated assuming repeated measures linear models, using maximum likelihood estimation (MLE) (SAS Proc Mixed).⁴⁰ All randomized participants, regardless of the extent to which they completed the intervention, will be included in intent-to-treat analysis. The benefits of this approach include: (1) all available data can be included in analyses; (2) correlation between related measures and adjusted test statistics can be estimated; (3) time varying covariates (such as school/employment status, treatment status (on treatment vs. completed), utilization of usual psychosocial care) can be incorporated into the model; and, (4) the assumptions about missing data from Missing Completely at Random (MCAR) to Missing at Random (MAR) are relaxed. Site will be included as a fixed effect. The primary hypothesis is that participants in Bright IDEAS-YA will experience greater decreases in depression and anxiety and increases in HRQOL at the 6month follow-up relative to participants in the enhanced usual psychosocial care condition. The primary endpoint will be the estimated change from baseline to 6 months in depression, anxiety, and psychosocial HRQOL (i.e., Social/Family Well-Being and Emotional Well-Being), calculated as linear contrasts of regression parameters using the main effect of time and the interaction between time and treatment group from the mixed linear model. The changes from baseline to 3 months, 12 months, and 24 months will be considered secondary endpoints. For HRQOL, we are particularly interested in 12-and 24-month followups given that changes may take longer to accrue compared with distress symptoms. Sensitivity analyses will be performed to determine the robustness of conclusions.⁴¹ Planned sensitivity analyses include: (1) analysis with and without adjusting for site; (2) per protocol analysis (excluding participants who did not complete at least 4 out of 6 intervention sessions, selected because it is expected that participants would have adequate exposure and practice with the Bright IDEAS model by four sessions); (3) adjustment for imbalance in baseline characteristics, if applicable; and (4) analysis to examine any differences by racial/ethnic subgroups.

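### Randomisation is stratified by site and age group, but the Aim 1 model names only site and gives neither stratum a time interaction, so the baseline-to-6-month contrast may forgo a little precision

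*Combined protocol and SAP*

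**What the plan says.** **Design.** Section 1.3 (Research Procedures) has the biostatistician "determine a randomization scheme stratified by site, age group (18-29 vs. 30-39", with an undisclosed block size, so that arms are balanced within site and age group. Allocation is 1:1.

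**Analysis.** For the Aim 1 repeated-measures model, section 6.1 states: "Site will be included as a fixed effect". No other randomisation factor is named. Sensitivity analysis (1) adds or removes site only. Sensitivity analysis (3) adjusts for baseline imbalance, but only where there is some. Section 6.1 also notes that "time varying covariates (such as school/employment status, treatment status (on treatment vs. completed), utilization of usual psychosocial care) can be incorporated into the model"; age group at randomisation is not such a variable.

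**Primary endpoint.** Section 6.1 obtains the change from baseline to 6 months from the repeated-measures fit: "calculated as linear contrasts of regression parameters using the main effect of time and the interaction between time and treatment group from the mixed linear".

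**Covariates elsewhere.** In the Demographic/Medical item of section 1.9, "Patients will report age, sex, independent living status, race, ethnicity, school/work status, health insurance coverage" and further items. The same item says that this information will describe the sample and serve as model covariates, with sex alone excepted. It does not say whether age enters as the 18-29 vs 30-39 stratum or as a continuous variable, or whether it interacts with time.

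**The concern.** Stratified blocking removes between-stratum variation from the treatment comparison. If the strata predict the outcome being compared and the model does not account for them, the model-based standard error still contains variation that the design has taken out. The test is then somewhat conservative and a little power is left unused.

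Here the outcome being compared is a within-person change. A stratum helps only if it predicts change, and only if the model lets its effect differ between baseline and 6 months. Neither 6.1 nor 1.9 provides that term for site or for age group. The two sections also leave the age term open: absent, continuous or grouped, with or without time. Two analysts could fit different primary models, each consistent with some part of the document.

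**Working it through.** **1. The plan's own power figure.** Section 1.5 gives 344 participants, 30% dropout, effect size 0.26 and 85% power for depression. With 344 × 0.70 / 2 ≈ 120 per arm and two-sided 5% (assumed; the section does not state alpha), a plain two-sample calculation gives Φ(0.26 × √(120/2) − 1.96) = Φ(0.054) = 52%. The stated 85% is not reproduced. That is a separate matter, which the age term does not explain. Below, 85% serves only as a starting point, and 52% is shown beside it.

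**2. Why a main effect cancels.** Write the mean for participant i at time t as time(t) + arm × time(t) + a × stratum(i). In the 6-month minus baseline difference, a × stratum(i) − a × stratum(i) = 0. A constant stratum term therefore leaves the contrast and its standard error unchanged with complete data, and nearly so with dropout. With a stratum × time term, a(6 months) − a(baseline) remains and absorbs variance of the change. This applies to site exactly as to age group. It assumes that baseline is one of the modelled outcomes and that the arms' baseline means are free to differ.

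**3. Size for age group.** Let R² be the share of the variance of the 6-month change explained by age group. The documents give no value, so a range is shown.

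- Overstatement of the standard error: 1/√(1 − R²)
- Actual size of a nominal 5% test: 2 × [1 − Φ(1.96/√(1 − R²))]
- Power once the term is added, from 85%: Φ((1.960 + 1.036)/√(1 − R²) − 1.960)

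| R² | SE overstated by | Actual size | Power from 85% | Power from 52.2% |
|---|---|---|---|---|
| 0 | 0% | 5.0% | 85.0% | 52.2% |
| 1% | 0.5% | 4.9% | 85.4% | 52.6% |
| 2% | 1.0% | 4.8% | 85.7% | 53.0% |
| 5% | 2.6% | 4.4% | 86.7% | 54.2% |

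**4. Check by simulation.** Assumptions: 344 participants, five surveys, SD 10, correlation 0.6 between surveys, three sites, and blocks of 4 within site × age group. Dropout, where present, is 30% at random, from 3 or 6 months onward. Each model was fitted by maximum likelihood with unstructured covariance, in 60 trials per row. Standard errors of the 6-month contrast are shown relative to the model with a site main effect only.

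| Dropout | Age-group difference in change | + age-group main effect | + age group × time |
|---|---|---|---|
| 0% | 0 points | 1.0000 | 0.999 |
| 0% | 3 points | 1.0000 | 0.984 |
| 30% | 0 points | 0.9998 | 0.998 |
| 30% | 3 points | 0.997 | 0.986 |

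The 3-point rows agree with step 3. The variance of change is 2 × 100 × (1 − 0.6) = 80, two equal age groups 3 points apart add 3²/4 = 2.25, R² = 2.25/82.25 = 2.7%, and √(1 − 0.027) = 0.986.

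**The case against.** The strongest reply is that the plan does not leave age out. Section 1.9 puts age first among the items to be used as covariates, and the site sentence in 6.1 can be read as saying how site is handled rather than as a complete list of terms. This stands. A reader might infer that the age stratum is ignored altogether, and the documents do not support that. What remains is that 6.1 does not carry the covariate over, and that neither section fixes its form or gives it a time interaction. Sensitivity analysis (3) does not close the gap, since stratified blocking should prevent the imbalance that would trigger it.

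A second reply is that naming age group beside site, in the way site is named, would change almost nothing. This also stands, and it is why the point concerns the stratum × time terms for both factors rather than the missing name alone.

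A third is that the gain is speculative. A reader might infer that power is certainly lost on every primary contrast. The documents do not show this: they give no variance share for either stratum, and the observational research cited in 1.9 found treatment and school or work status, rather than age, to be the main drivers of distress. The 3-point difference simulated above (0.30 SD) is numerically larger than the planned effect size of 0.26, although the SD units may differ. The loss must therefore be stated as conditional.

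**Conclusion.** The point holds as a minor, free improvement. The randomisation uses two strata, the Aim 1 model names one, and neither has the time interaction that a change-from-baseline contrast needs in order to benefit.

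For age group, the model-based standard error is about 0.5-2.6% too large if the stratum explains 1-5% of the variance of the 6-month change. That is worth 0.4 to 1.7 percentage points of power from the stated 85%. If age group does not predict change, the gain is nil. For site the same formula applies, and the documents give no figure to put into it.

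The R² range is an assumption. The cancellation rests on the contrast as 6.1 describes it, with baseline among the modelled outcomes and the arms' baseline means unconstrained. Omitting the terms introduces no bias and does not inflate the type I error: the test runs at or slightly below its nominal level. No conclusion of the trial is put at risk.

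**What to change.** In section 6.1, replace the sentence on site with wording such as: *Both randomisation strata, site and age group (18-29 vs 30-39, as used for randomisation), will be included as fixed effects, each with its interaction with time, in the Aim 1 model for every outcome.* Word sensitivity analysis (1) for both strata. In section 1.9, say which of the listed items enter the primary model and in what form, so that age is not specified in two ways. Settle this before unblinded data are analysed.

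The cost is a few lines of text. The stratum should already be held in DatStat, because assignment follows the stratified scheme loaded there. With three sites and five surveys, the change adds 2 × 4 = 8 parameters for site × time and 1 + 4 = 5 for age group and its interaction, 13 in all, which 344 participants support easily.

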1.5 Sample Size Justification

Up to 344 YA patients newly diagnosed with cancer will be enrolled across sites. There are no exclusion criteria based on gender or race. We expect the percentage of male/female and minority race participants enrolled to reflect the distributions seen at three sites.

Power focused on Aim 1 and was calculated based on effect size estimates that incorporate both estimates of change in mean as well as standard deviations from our pilot data and compared against published data, assuming an intent-to-treat analysis. For the proposed study, we assume the standard deviation will be 70% of the pilot standard deviation, due to tightening of the eligibility criteria to exclude those with cancer recurrence and recruit within 4 months of first diagnosis. In addition, we assume that the control group will see 20% of the change in depression compared to intervention. This leads to a Cohen effect size of 0.26. Assuming 344 subjects with 30% dropout, we will have 85% power to detect an effect of intervention on the Depression score. Similar calculations demonstrate 82% power to detect an effect of intervention on Anxiety. If we observe a group difference closer to 3.22 for Depression, cited as clinically meaningful in previous literature,²³ then under the assumptions listed above, our Cohen effect size will be closer to 0.29 and our power for the primary outcomes will be higher. For HRQOL, pilot Cohen estimates of effect size and estimates from the literature with the assumptions above would yield a Cohen effect size of 0.32, which would yield a power of 95%.²⁴²⁵

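### Section 6.1 does not constrain arm means to be equal at baseline or adjust for the baseline score; if baseline is left free, the primary 6-month contrast is less precise than the same data allow

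*Combined protocol and SAP*

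**What the plan says.** Section 6.1 (Aim 1) evaluates efficacy "assuming repeated measures linear models, using maximum likelihood estimation (MLE) (SAS Proc Mixed"), and gives as one benefit that "all available data can be included in analyses". The primary endpoint, for depression, anxiety and the two psychosocial FACT-G subscales, is the change from baseline to 6 months, "calculated as linear contrasts of regression parameters using the main effect of time and the interaction between time and treatment group". Baseline is therefore one of the repeated outcomes.

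On adjustment, Section 6.1 says "Site will be included as a fixed effect", and lists among the sensitivity analyses "3) adjustment for imbalance in baseline characteristics, if applicable". The baseline value of the outcome is not named in either place.

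Section 1.3 A has participants complete the baseline survey before they are randomised, under a "randomization scheme stratified by site, age group (18-29 vs. 30-39 based on definitions of emerging adults and young adults"). Section 6.1 names site but not age group. Section 1.9, under Demographic/Medical, begins "Patients will report age, sex, independent living status" and says these variables will be covariates in the model (sex excepted). It does not say whether age enters as a continuous variable or as the two randomisation groups, or whether the model meant is the Aim 1 model.

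**The concern.** Because baseline is measured before randomisation, the true arm means at baseline are equal by design. A model that estimates a separate baseline mean in each arm, and then subtracts it, carries the chance baseline difference into the change contrast in full. A model that holds the two means equal, or conditions on the baseline score, removes only the part that the correlation justifies. Both estimate the same treatment effect; the second has the smaller SE whenever the correlation is below 1.

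The text does not say which model is meant. Two competent analysts could fit different primary models from it and report different estimates and SEs. At stake are precision and pre-specification, not bias or type I error.

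**Working it through.** **1. What the named terms imply.** There are five visits and two arms, so ten visit-by-arm means. With visit and arm as class effects, the design matrix has these ranks:
- visit + visit x arm: 10
- visit + arm + visit x arm: 10
- visit + visit x arm at post-baseline visits only: 9

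Omitting the arm main effect therefore does not constrain baseline under class coding. With numeric time starting at 0, or reference coding with baseline as the reference, time and time x arm alone would constrain it. Section 6.1 states no coding.

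**2. Inputs.** From Section 1.5: "Assuming 344 subjects with 30% dropout", effect size 0.26 and 85% power for depression. From Section 1.3 A: 1:1 allocation. So n = 344/2 = 172 baselines per arm and, if the 30% are lost by 6 months, m = 172 x 0.7 = 120.4 per arm at 6 months. Assumed, because not stated: baseline-to-6-month correlation rho, two-sided alpha of 0.05, outcome SD of 1, and the timing of dropout.

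**3. The plan's own figure.** A plain two-sample comparison with d = 0.26 and 120.4 per arm has power Phi(0.26 x sqrt(120.4/2) - 1.96) = 52%, not 85%. The stated figure needs a correlation that the documents do not give (step 6).

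**4. Formulas.** Variance per arm of the 6-month contrast:
- free baseline: (1 - rho^2)/m + (1 - rho)^2/n
- equal baseline means: (1 - rho^2)/m

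The ratio of SEs, free to constrained, is sqrt(1 + (m/n)(1 - rho)/(1 + rho)).

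**5. Results.** The SE of the arm difference is sqrt(2 x variance per arm). With m/n = 0.7:

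| rho | SE free | SE constrained | SE excess | SE excess, nobody lost by 6 months (m/n = 1) |
|---|---|---|---|---|
| 0.3 | 0.1443 | 0.1229 | 17.3% | 24.0% |
| 0.5 | 0.1240 | 0.1116 | 11.1% | 15.5% |
| 0.7 | 0.0976 | 0.0920 | 6.0% | 8.5% |
| 0.8 | 0.0803 | 0.0773 | 3.8% | 5.4% |

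A five-visit calculation using all available data, with retention of 0.85 at 3 months and 0.70 from 6 months on, gives excesses of 17.5%, 11.3%, 6.2% and 4.0% under compound symmetry, and 18.0%, 11.7%, 6.5% and 4.1% under AR(1). If the 30% loss is spread out to 24 months (retention 0.90/0.85/0.80/0.70, so 15% already lost at 6 months), compound symmetry gives 20.8%, 13.4%, 7.3% and 4.7%.

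**6. The correlation that fits the stated power.** Take 0.26 as raw SD units, two-sided 0.05 and a free baseline. Setting 0.26/SE - 1.96 equal to the normal quantile for 85% gives rho = 0.765 by the step 4 formula; the five-visit versions give about 0.75 to 0.76, and an analysis of completers alone about 0.77. At rho = 0.765 the SEs are 0.0868 and 0.0830, an excess of 4.6%, and constraining baseline moves power from 85% to 88%.

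**7. Age group.** An age-group difference of delta SD adds 0.25 x delta^2 to every element of the covariance matrix. For assumed delta of 0.2 to 0.5, fitting age group changes the SE by at most about 0.3% with a free baseline and 1.6% with a constrained one.

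**The case against.** The strongest reply is that no error has been shown. A free baseline is a legitimate model under randomisation, it suits a likelihood analysis of all available data, and the text never commits to it: Section 6.1 names no arm main effect, and the rank argument needs class coding that the section does not state. This stands. A reader might infer that the plan has chosen the less efficient model; the documents do not support that, so the loss must be stated conditionally.

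A second reply is that the large percentages come from correlations that sit poorly with the plan's own power: at rho of 0.3 or 0.5 the free model has about 44% or 56% power against the stated 85%. This also largely stands. The figure closest to the plan's own assumptions is 4 to 5%, not 11 to 17%. It does not establish rho, because alpha, sidedness and the SD behind the effect size are not given, and the four outcomes need not share one correlation.

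A third reply is that a baseline covariate would do as well. That is right. Participants with only a baseline score add essentially nothing to the 6-month treatment difference, so keeping them is no strong reason to prefer the constrained model.

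On age, Section 1.9 already places it among the model covariates. What remains is that its form and the model concerned are not stated.

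**Conclusion.** The point holds as a no-cost improvement in precision and a gap in the specification of the primary model. Section 6.1 does not fix the baseline mean structure. If visit and arm are class effects, baseline is free, and the SE of the primary contrast is larger by about 17%, 11%, 6% or 4% at assumed rho of 0.3, 0.5, 0.7 or 0.8 with 30% lost by 6 months, or about 24%, 15%, 8% or 5% with no loss by then. At the correlation of about 0.75 to 0.77 that would reconcile the stated 85% power with an effect of 0.26 raw SD at two-sided 0.05, the excess is about 4 to 5% with 30% lost by 6 months. If the intended coding constrains baseline, there is no loss.

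Two stronger readings should be resisted. A reader might infer bias or an inflated type I error; neither follows, since both models estimate the same effect validly under randomisation. A reader might also infer from the 52% in the working that the stated power is wrong; the inputs needed to verify it are missing, so it can be neither confirmed nor refuted. Age group belongs in the model for consistency with the stratified design, not for any material gain in precision.

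**What to change.** In Section 6.1, specify the primary model in one of two ways:
- visit plus treatment x visit at post-baseline visits only, so that baseline means are equal across arms. State the coding, because dropping the arm main effect alone does not achieve this with class effects.
- equivalently for this purpose, post-baseline scores as the outcome, with the baseline score and its interaction with visit as covariates.

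Take the 6-month treatment difference as the primary contrast. Include both stratification factors, site and age group (18-29/30-39), as fixed effects. Align Section 1.9 with this by stating the form of age, and which of the listed covariates enter the primary model rather than only the sensitivity analysis for baseline imbalance.

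The cost is model wording and coding. The baseline scores and age are already collected, and neither the sample size nor the visit schedule changes.

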■ Subject Identifiers: We will collect participant name, address, telephone number, and email address for contact purposes throughout the study. Each participant will be assigned a participant ID number and we will keep a key linking the ID number to name for up to 6 years after the close of the study. We will collect MRN, date of birth, and date of diagnosis to abstract medical treatment data, calculate age, and calculate time since diagnosis. At the conclusion of the study, identifiers will be removed from the database and de-identified data kept indefinitely.

B. Secondary Data Collection

- Type of Records: Medical records will be accessed to abstract: date of birth, date of diagnosis, type of diagnosis to determine eligibility and describe the study sample. At the last survey follow-up, records will be accessed to document treatment(s) received, relapse status, comorbid psychological conditions, any documented social concerns, hospice referral, COVID-19 vaccination history, and use of psychosocial services. For those subjects who do not remain in the study until last follow-up due to various reasons (e.g., no longer interested, deceased, etc), data abstraction will occur at time subjects are exited from the study or as soon as practical.
- Location: Research staff with authorization to access medical records will access the medical records at each site using an authorized workstation to access the record.
- Inclusion/Exclusion: See Inclusion/Exclusion criteria in section 4.1C.
- Data Abstraction Form(s): See Data Abstraction Form.

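### None of the four named sensitivity analyses varies the missing-at-random assumption, so their agreement could not show that a positive 6-month result withstands informative dropout

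*Combined protocol and SAP*

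**What the plan says.** Section 6.1 (Aim 1) bases efficacy on a repeated-measures linear model fitted by maximum likelihood, with all randomized participants included. One listed benefit concerns missing data: "the assumptions about missing data from Missing Completely at Random (MCAR) to Missing at Random (MAR) are relaxed". The primary contrast is the change from baseline to 6 months in depression, anxiety, and social/family and emotional well-being.

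The same section says "Sensitivity analyses will be performed to determine the robustness of conclusions" and names four:

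1. with and without adjustment for site;
2. per protocol, excluding participants with fewer than 4 of 6 sessions;
3. adjustment for baseline imbalance, if applicable;
4. differences by racial/ethnic subgroup.

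On the expected loss, section 1.5 says: "Assuming 344 subjects with 30% dropout, we will have 85% power to detect an effect of intervention on the Depression score". It does not say at which survey the 30% applies or how it divides between arms.

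Section 1.9 (Secondary Data Collection) abstracts from the medical record, among other items, "relapse status, comorbid psychological conditions, any documented social concerns, hospice referral". This is done at the last follow-up, or around the time of exit for those who leave early.

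**The concern.** MAR means that, given the data the model has seen, whether a 6-month score is missing does not depend on the score itself. Here the outcomes are self-reported distress and well-being during cancer treatment. Section 1.6 expects that some patients will at times be too ill for a session, and section 1.9 foresees exit through loss of interest or death. Only one arm is asked to attend six 45-minute sessions, so the reasons for leaving may differ by arm. Dropout that depends on the unseen score is therefore plausible, and so is a difference between arms.

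The four checks do not address this. Analyses 1 and 3 change the covariates and keep MAR. Analysis 2 can remove only intervention participants, because controls have no sessions; it adds selection and leaves the assumption about missing surveys as it was. Analysis 4 is a subgroup question. If all four agreed with the primary result, the report could call the result robust although its most exposed assumption had not been varied.

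**Working it through.** **Inputs from the plan (section 1.5, and 1:1 allocation in section 1.3).** 344 randomized; 30% dropout, so 344 × 0.70 / 2 ≈ 120 per arm; planned depression effect 0.26 SD; stated power 85%; 3.22 points corresponds to 0.29 SD, so SD = 3.22 / 0.29 = 11.1 points.

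**Assumptions.** Two-sided alpha 0.05 (the documents state none). The share missing at 6 months, m, is 30%, or 15% if the 30% accumulates over 24 months. Intervention-arm dropouts are worse than MAR predicts by delta, and control dropouts are as MAR predicts.

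**The plan's own figure.** A plain comparison of 120 per arm has SE = √(2/120) = 0.1291 SD. At 0.26, z = 0.26 / 0.1291 = 2.01 and power is Φ(2.01 − 1.96) ≈ 52%, not 85%. The SE implied by 85% power is 0.26 / (1.960 + 1.036) = 0.0868 SD. A baseline-adjusted analysis of 120 per arm would reach this with a correlation of about 0.74, which the documents do not state. The 85% is thus not reproducible from the stated inputs, but it is not shown to be wrong. Both SEs are carried forward.

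**Formulas.**
- Bias in the contrast = m × (intervention delta − control delta), here m × delta.
- Type I error = Φ(−1.96 + bias/SE) + Φ(−1.96 − bias/SE).
- Tipping shift for an observed 0.26 = (0.26 − 1.96 × SE) / m. The numerator is 0.26 − 0.2530 = 0.0070 with SE 0.1291, and 0.26 − 0.1701 = 0.0899 with SE 0.0868.

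| Missing at 6 months | SE | Bias at delta 0.3 SD | Type I error | Tipping shift for 0.26 |
|---|---|---|---|---|
| 30% | 0.129 | 0.09 SD | 11% | 0.02 SD = 0.3 points |
| 30% | 0.087 | 0.09 SD | 18% | 0.30 SD = 3.3 points |
| 15% | 0.129 | 0.045 SD | 6% | 0.05 SD = 0.5 points |
| 15% | 0.087 | 0.045 SD | 8% | 0.60 SD = 6.7 points |

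A bias of 0.09 SD is 0.09 / 0.26 = 35% of the planned effect.

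**If intervention dropouts gain nothing.** The effect becomes 0.26 × (1 − m). With m = 30% and SE 0.087 it is 0.182, z = 2.10, and power falls from 85% to about 56%.

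**Would the planned checks notice?** A simulation took a true effect of zero, 344 participants, 30% missing per arm and a baseline-to-6-month correlation of 0.7 (assumed). Control dropout was random; intervention dropout depended on the unseen 6-month score. Regression on baseline in observed cases stood in for the likelihood model. With log-odds of 0, 0.5, 1.0 and 1.5 per SD, the false effect favouring the intervention was 0.00, 0.07, 0.13 and 0.18 SD, and the chance of a significant result in its favour was 3%, 12%, 30% and 50%. At 1.5, the without-site, per-protocol and baseline-adjusted versions gave 51%, 49% and 50%. Site and the added covariate were simulated as unrelated to the outcome, and session completion rates were assumed, so this shows that the checks can agree with a biased result, not that they always would. The subgroup analysis was not simulated.

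**The case against.** MAR is stated openly and is a reasonable primary assumption. Baseline scores and any 3-month scores inform the likelihood. Section 6.1 allows treatment status and use of psychosocial care as time-varying covariates, and sections 1.3 and 4.6 set out reminders, payments and other retention measures. The list of sensitivity analyses is worded as open. All this stands, and it makes MAR more credible. It does not test MAR: self-reported service use is missing whenever the survey is missing, and an analysis added after the data are seen is not prespecified.

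Several stronger readings are tempting, and the documents do not support them:

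- **That a positive result could rest entirely on MAR.** With 30% missing, about 70% are still observed. Bringing 0.26 to zero needs intervention dropouts to be 0.26 / 0.30 = 0.87 SD (9.6 points) worse than predicted. Statistical significance is more fragile than the estimate.
- **That a shift of about 0.3 points is enough to overturn the result.** That figure needs SE 0.129, at which 0.26 is barely significant to begin with, and which conflicts with the stated 85% power. With the SE implied by that power, the shift is 3.3 points.
- **That 30% will be missing at 6 months.** The plan gives no time point. Follow-up runs to 24 months, so the loss at 6 months may be smaller.
- **That illness and relapse alone imply bias.** They act in both randomized arms, and equal shifts with equal dropout cancel in the contrast. The figures above are for a shift in one arm.
- **That the abstracted record data are ignored.** Section 1.9 assigns diagnosis and treatment received to covariate use. The gap concerns relapse, hospice referral and psychological conditions, which are not linked to the missing-data analysis.

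**Conclusion.** The point holds as a gap in the sensitivity plan. It is not a fault in the primary model. None of the four named analyses varies MAR, and no other section supplies one that does, so their agreement cannot support a claim of robustness to informative dropout.

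The size is uncertain, and the range should be reported as such. For an intervention-only shift of 0.3 SD, type I error runs from about 6% (15% missing, SE 0.129) to 18% (30% missing, SE 0.087). An observed 0.26 loses significance at 0.3 to 3.3 points with 30% missing, and at 0.5 to 6.7 points with 15% missing. These figures rest on an SD of 11.1 points, two-sided 5% testing, a shift in one arm only, and a 6-month loss that the documents do not give. The width of the range is itself a reason to plan the analysis in advance. This should be changed; it does not invalidate the design.

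**What to change.** In section 6.1, add a prespecified missing-not-at-random sensitivity analysis for each 6-month primary outcome (depression, anxiety, social/family well-being, emotional well-being):

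- Multiple imputation by arm, followed by delta adjustment towards worse scores. Shift intervention-arm dropouts first, then, separately, dropouts in both arms, in steps scaled to each outcome's SD until significance is lost.
- A control-based imputation for intervention-arm dropouts.
- A report of the tipping point, with dropout and its reasons by arm and visit. Judge plausibility on each outcome's own scale. The 3.22 points in section 1.5 is a between-group difference cited for depression only, so it should not serve as a fixed pass mark for dropout shifts or for the FACT-G subscales.
- Abstracted record variables as auxiliaries only where they can be dated to on or before 6 months in both completers and early leavers. Abstraction takes place at last follow-up for completers and around exit for early leavers, so undated relapse or hospice entries would cover different windows.

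The cost is SAP wording and some programming, plus event dates where abstracted variables are used. No added patients or visits are needed. The downside is that a positive result may have to be described as sensitive to missing data.
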